**7.3 PROTOCOL DEVIATIONS**

A protocol deviation is defined as an event where the Investigator or site personnel did not conduct the study according to the protocol or a failure to adhere to the IRB/HREC reporting procedures and policies.

The study sponsor reserves the right to terminate an investigator/investigational site for any of the following reasons:

- Failure to secure participant informed consent including protection of personal data prior to enrollment.
- Failure to report serious adverse device effects within 24 hours of discovery.
- Repeated investigational plan deviations.
- Repeated failure to appropriately complete case report forms.

- Failure to enroll participants within the planned enrollment period.
- Loss of or unaccounted for investigational product inventory.

### 7.3.1 Investigator Reporting

Deviations must be reported regardless of whether medically justifiable or taken to protect the subject in an emergency. Participant specific deviations will be reported on the Protocol Deviation eCRF. Non-subject specific deviations, (e.g. unauthorized use of a study device outside the study, unauthorized use of a study device by a physician who has not signed an Investigator agreement or not been trained in the use of the device, etc.), will be reported to directly to the study sponsor. Any serious breaches of the protocol or the conditions and principles of GCP in connection to this trial will be reported to the IRB/HREC in accordance with their reporting policies and procedures. A serious breach is likely to impact to a significant degree: (a) the safety or physical well-being of the participants of the trial; or (b) the scientific value of the trial.

All major deviations will be reported to the Sponsor within 24 hours of the Investigator becoming aware.

Protocol deviations to the inclusion/exclusion criteria and deviations that affect the primary endpoints are considered major protocol deviations. Protocol deviations that may affect the secondary endpoints are considered minor protocol deviations.

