**Table 1 Schedule of Events**

Protocol Requirements	Screening / Baseline	Pre-Procedure	Procedure	24-hours	7 Days	1 Month 	3 Months 	6 Months	12 months
		Day 0	Day 0	18-48 hours Remote	± 3 days Remote or Clinic	+ 2 weeks Clinic	-2 weeks-+ 4 weeks Clinic	± 4 weeks Clinic	± 4 weeks Clinic
Informed Consent 	X								
Demographics	X								
Inclusion/Exclusion Criteria	X	X							
Medical and surgical history	X								
BMI	X					X	X	X	X
Participant Reported Questionnaires  :									
Procedure Goals	X						X	X	X
Recovery 				X	If indicated	If indicated	If indicated	If indicated	If indicated
Discomfort and Soreness, Pain VAS 			X 	X	X	X	X	If indicated	If indicated
QOL and Satisfaction							X	X	X
Participant Symptom Diary 				X	X	X			

 30 days is also referred to as 1-month visit

 For purposes of scheduling, the protocol definition of a month is 30 days. Week refers to 7 days.

 Prior to any study specific procedures; participant may need to be re-consented if protocol is amended.

 Participants should complete via their private ePRO login with the exception of Pain VAS at procedure and Discomfort, Soreness Pain VAS questionnaires if indicated after 3M visit.

 Administered until participant returns to normal activities.

 Daily completion of Discomfort, Soreness and Pain VAS through 7 days post-procedure.

 Only VAS Numeric Pain Distress Scale administered during and after the procedure (before discharge).

 Participants to complete weekly, four (4) times through 28 days post-procedure.

Abbreviated CONFIRM Protocol

Protocol Requirements	Screening / Baseline	Pre-Procedure	Procedure	24-hours	7 Days	1 Month 	3 Months 	6 Months	12 months
		Day 0	Day 0	18-48 hours Remote	± 3 days Remote or Clinic	+ 2 weeks Clinic	-2 weeks+ 4 weeks Clinic	± 4 weeks Clinic	± 4 weeks Clinic
Physical Exam 	X								
Standard Photography	If done				If Clinic 				
Study Photography		X 				X	X	X	X
Marking the insertion sites and depressions to be treated		X							
Pregnancy test 		X							
Vitals		X							
Deployable Hook Procedure			X						
Con. Medications/ Treatments	Captured and Updated From -30 days to Study Exit								
Adverse Event  Assessment	Monitored throughout study								

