##### 4.1 MEDICAL PHOTOGRAPHY

Digital photography will be utilized in the assessment of the primary endpoint and other efficacy measurements at the intervals outlined in **Table 1**. The evaluations will occur in advance of each planned interim analysis as outlined in **Table 3**, and will follow the order outlined to ensure no pre-mature unblinding of the before/after that is required for the GAIS evaluation.

The medical photography which the independent evaluators will use, with a prescribed methodology, is distinguished here with name “Study Photography”, is described below.

Photographs captured outside of the study photography protocol, using methods normally used if not in a trial, will be included in the study dataset, but not utilized for endpoints, and will be referred to as “Standard photography”.

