#### 4.1.1 Study Photography

The study endpoint relies on quality and consistent imaging. As such, it is imperative the images are taken under strict, standardized environments with only qualified photographers that are trained to the same methods. The Sponsor will ensure photographers are available for each site throughout the study and, if necessary, provide a contracted medical photographer. A chief photographer will be identified to develop and conduct training for all study site photographers. The training manual will outline the specific set-up including equipment, lighting, participant angles, and camera positioning.

Participants will be given reminders to wear loose fitting clothes without seams on the buttock or posterior thigh portions of the clothes before each required study photography visit and to prepare to stand until compression lines disappear, if present.

Prior to uploading images into the study database, the image metadata will be modified to include the participant ID and any date, location. PHI will be redacted.

For each photo session, the participant will stand and wear the provided standardized photographic garment as described in the CONFIRM imaging protocol. The participant will be instructed to relax muscles and stand at ease.

All study photography from this study are the property of the Sponsor and may be utilized for clinical development, scientific communication, marketing, regulatory purposes, and/or legal applications as required/desired by the Sponsor.

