## 6 STATISTICAL METHODS

### 6.1 STATISTICAL AND ANALYTICAL PLANS

#### 6.1.1 Analysis Cohorts

- **Modified Intent-to-Treat (mITT) Cohort:**

The modified intent-to-treat mITT data set will include all enrolled participants that underwent the DH procedure but exclude any roll-in participants. The mITT analysis cohort will be used for all described analyses.

- **Per Protocol (PP) Cohort:**

The PP cohort will be used as a secondary support of the primary effectiveness m-ITT analysis and may be used in exploratory analysis.

The PP analysis set will exclude participants with the following significant protocol deviations:

- 1) Participants with significant violations of the inclusion and exclusion criteria, including:
  - Mild cellulite
  - Impactful co-morbidity outlined in eligibility criteria
  - BMI >30.1
  - Pregnancy or weight gain/loss >10% of baseline weight
- 2) Participants who do not have images for primary effectiveness endpoint (missed, COVID-19, etc.)

Overall, protocol deviations for active participants will be summarized by severity (major/minor), type by visit, and by site. Any deviations or issues reported to IRB/HREC and will be described.

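### The Per Protocol set is an incomplete check on the primary result: mistimed or faulty 3-month study photographs stay in, and its BMI limit does not match exclusion criterion 10

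*Combined protocol and SAP*

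**What the plan says.** Section 6.1.1 gives the PP set its role: "The PP cohort will be used as a secondary support of the primary effectiveness m-ITT analysis". It introduces the exclusions with "The PP analysis set will exclude participants with the following significant protocol deviations", and lists two.

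- The first is "Participants with significant violations of the inclusion and exclusion criteria, including", followed by mild cellulite, impactful co-morbidity, BMI above 30.1, and pregnancy or a weight change of more than 10% from baseline.
- The second is "Participants who do not have images for primary effectiveness endpoint (missed, COVID-19, etc".

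*Significant* is not defined and is not tied to any other grading.

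Section 7.3.1, which deals with reporting by investigators, does grade deviations: "Protocol deviations to the inclusion/exclusion criteria and deviations that affect the primary endpoints are considered major protocol deviations". In the analysis, the major/minor grade is used only for descriptive summaries (6.1.1 and 6.9).

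Four other places matter:

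- Exclusion criterion 10 in 2.2 bars BMI of 30.0 or above.
- Table 1 sets the 3-month visit window at -2 to +4 weeks.
- On study photography, 4.1.1 says "it is imperative the images are taken under strict, standardized environments". Section 4.1 says that photographs made by a clinic's usual methods "will be included in the study dataset, but not utilized for endpoints".
- The primary analysis is a t-test on the change in CSS in mITT (6.3.3, 6.3.4). Imputation of a missing 3-month CSS appears in 6.4 as a sensitivity analysis.

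**The concern.** The primary endpoint is read entirely from photographs, so the timing and technique of the 3-month session are the obvious ways for conduct to affect it. A PP analysis offered as support should show whether the result survives without participants whose assessment was mistimed or technically deficient. As written, it keeps them. The one rule that mentions images concerns their absence, which the mITT t-test already handles by having no value to analyse.

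The eligibility part has a smaller flaw of the same kind: the PP BMI limit is looser than the entry limit, so someone who should not have been enrolled can be counted as per protocol.

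At stake is how far agreement between mITT and PP can be relied on. If mistimed or faulty images, or a few ineligible participants, shift the mean change, they shift it in both sets. Agreement would then say little about that source of error.

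**Working it through.** The plan gives no figure on this point: no expected number of deviations, and no SD for the change in CSS. The check is therefore mainly a comparison of rules. The sample sizes used below come from 6.3.7 and the synopsis: 54 evaluable; 54 × 1.25 = 67.5, rounded up to 68; and 74 − 6 roll-in = 68, which agrees.

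**Step 1. Rules side by side.**

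| Situation | Grade under 7.3.1 | PP rule in 6.1.1 | In the unimputed mITT t-test? |
|---|---|---|---|
| No 3-month images | – | Removed (second rule) | No: no change score |
| Only clinic-standard photographs | – | Removed, if read with 4.1 (no endpoint image) | No |
| Study photographs outside the window | Major, if the primary endpoint is affected | No rule | Yes |
| Study photographs with a method fault, still scored | Major, if the primary endpoint is affected | No rule | Yes |
| BMI 30.0 to 30.1 | Major | Not removed by the BMI item | Yes |
| BMI above 30.1, mild cellulite, impactful co-morbidity | Major | Removed | Yes |
| Weight change above 10% of baseline | Not itself an entry criterion (criteria 3 and 4 concern intent and the prior six months) | Removed | Yes |
| Other eligibility breach | Major | Removed only if judged significant | Yes |

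**Step 2. What the image rule contributes.** Let M be the mITT participants with both baseline and 3-month CSS. The t-test uses M. PP is mITT minus those caught by the first rule, minus those without images, which equals M minus those caught by the first rule. The second rule cancels, so PP differs from the analysed mITT set only through the first rule. This assumes that the primary t-test is unimputed, as 6.4 implies.

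**Step 3. The window in days.** Table 1 defines a month as 30 days. The nominal visit is day 90, and the window runs from 90 − 14 = day 76 to 90 + 28 = day 118. Nothing in 6.1.1 refers to these limits.

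**Step 4. Width of the BMI gap.** Ineligible at 30.0 or above and removed by the PP item only above 30.1 leaves 30.0 to 30.1 inclusive, a band of 0.1 kg/m². In weight this is 0.1 × height²:

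- 1.55 m: 0.24 kg
- 1.65 m: 0.27 kg
- 1.75 m: 0.31 kg

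The heights are assumed. The band is narrow enough that few participants, if any, should fall in it.

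**Step 5. Illustrative shift in the mean.** If *k* of *n* participants differ from the rest by *d* points on average, keeping them moves the mean by (*k*/*n*) × *d*. With *d* = 1 (assumed, in either direction):

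| *k* | *n* = 54 | *n* = 68 |
|---|---|---|
| 1 | 0.019 | 0.015 |
| 3 | 0.056 | 0.044 |
| 5 | 0.093 | 0.074 |

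These figures show scale only. Neither *k* nor *d* can be taken from the documents.

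**The case against.** The case on the other side is substantial, and much of it stands.

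- *Section 7.3.1 does not define PP.* It is a reporting rule that triggers 24-hour notice to the sponsor. A reader might infer that 7.3.1 and 6.1.1 contradict each other; they do not. They are unaligned. A PP set that removes only some reportable deviations is a normal choice: under 7.3.1 even herbal tea within 14 days of the procedure is major, and that need not affect CSS.
- *PP is not empty.* A reader might infer that it cannot test the primary result against major deviations at all. The list does not support that: mild cellulite, impactful co-morbidity and BMI above 30.1 all lead to removal, and so does a weight change above 10% during follow-up.
- *The eligibility list is open.* It is introduced as examples, so an unlisted breach, including BMI 30.0 to 30.1, could be removed if judged significant. That is correct, but it leaves the judgement undefined and undated, and it does not extend to the separate image rule.
- *Non-protocol photographs are already barred.* Section 4.1 keeps standard photographs out of the endpoints, so the gap does not cover every off-protocol image. But 4.1 describes photographs made by methods used outside a trial. It does not address a study session held late or with a fault in lighting, angle or camera position. The separate imaging protocol, which is not available here, may contain acceptance rules.
- *CSS is read blind, with image order randomised.* Nothing in the documents says that late or faulty images would favour the device. A reader might infer a raised risk of false success. That would need an SD, a deviation rate and a one-directional bias, none of which the documents give. The success rule in 6.3.5 also applies to mITT, which a change to PP does not touch.

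**Conclusion.** The point holds as a limited one. PP as written is an incomplete check on the primary result. Its image rule removes nobody from the unimputed mITT t-test, and 3-month study photographs that are out of window or not to method have no exclusion. Treating these as major deviations rests on a natural reading of 7.3.1, which gives no examples. The BMI mismatch is certain from the text, but its effect should be very small.

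The size of the image gap cannot be computed from the documents. The illustrative shifts of 0.015 to 0.093 points rest on an assumed one-point difference and one to five affected participants, with no presumption about direction. The matter is confined to a supportive analysis. The mITT test, its alpha and the sample size stay as they are, and no type I error figure should be offered as a benefit of the change. It is worth making because it is cheap and makes agreement between mITT and PP more informative.

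**What to change.** Amend 6.1.1 in four respects:

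1. Add as PP exclusions 3-month study photography outside the Table 1 window, and 3-month study photography with a documented departure from the imaging method. If the contingency in 6.3.6 moves the endpoint to 6 months, apply the same rule to that visit.
2. Reconcile the PP BMI limit with exclusion criterion 10.
3. State which other major eligibility deviations count as *significant*. This need not be all of them; the test is whether the breach could plausibly affect CSS.
4. Freeze the PP list before CSS readings are linked to time point. Section 6.3.6 already has a count of available images before the blinded reading, which is a convenient moment.

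The cost is SAP wording, a slightly smaller PP set and a somewhat wider interval in a supportive analysis.

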## 7.4 STUDY DEVICES

### 7.4.1 Labeling

The study sponsor will label all study devices in accordance with FDA regulations per 21CFR 812.5 and other local regulatory requirements where the study is being conducted.

### 7.4.2 Ordering and Storing Study Device

Study devices will be stored in a secure area, where only study personnel can access. The PI or designee will be responsible for maintaining control of and verifying each device's disposition.

### 7.4.3 Study Device Accountability

The Investigator shall maintain adequate records of the receipt, use, and disposition of the study device.

Study devices will only be used with this clinical investigation. The PI or an authorized designee shall keep device accountability log tracking documenting the receipt, use, return and disposal of the study devices, which shall include:

- a) the date of receipt and the signature of the individual who received the product(s),
- b) identification of each study device (batch number/serial number or unique code),
- c) the expiry date, if applicable,
- d) the date or dates of use,

- e) unique participant identification number,
- f) date when the study device was returned (for any reason), and
- g) the date of return of unused, expired or malfunctioning study devices, if applicable.

This log must be maintained at each investigational site and must be filed in the regulatory binder. At the end of enrollment, the study sponsor or designee shall ensure that documentation of the final reconciliation of all devices is signed or initialed by the PI or authorized designee.

#### **7.4.4 Device Disposal or Return**

Devices are to be disposed of utilizing clinic specific biohazard procedures unless return is required or requested by the sponsor. Details outlining study sponsor returned goods policy will be provided in the training materials. The site will return all unused devices remaining at the end of the enrollment period.

### **7.5 FINANCIAL DISCLOSURE**

All Investigators must provide the sponsor with documentation of financial interest related to the study sponsor. Investigators must complete and provide Financial Disclosure in compliance with 21CFR 812.43 (c) (5) to the sponsor during the approval process of the site and maintain this documentation throughout the study and for 1 year following completion of the study.

### **7.6 PARTICIPANT PRIVACY**

The Investigator agrees to comply with all applicable local regulations relating to the privacy of participants' health information, including, but not limited to, the Standards for Individually Identifiable Health Information, 45 CFR Parts 160 and 164 and in accordance with the Health Insurance Portability and Accountability Act of 1996 (HIPAA), which states all participants should be informed of potential uses and disclosures of their medical information for research purposes, and their rights to access information about them by covered entities. Each Investigator will follow the procedures for securing HIPAA compliance as directed by their respective IRB/HREC or Privacy Board, and to obtain written authorization to use and disclose participant information for all clinical research and research involving questioning of the participant's or participants' physician(s). Per individual site procedures, this authorization may be included as part of the participant informed consent form.

The Investigator agrees to maintain all essential study documents and source documentation, in original format, that support the data collected on the study participants in compliance with the ICH/GCP guidelines (the Investigator's File, including signed Informed Consent forms and participant-related materials) in a location that is secure and to which access can be gained if required.

Participant confidentiality will be maintained throughout the clinical investigation in a way that ensures the information can always be tracked back to the source data. For this purpose, a unique participant identification code will be used that allows identification of all data reported for each participant. Data relating to the clinical investigation might be made available to third parties (for

example in case of an audit performed by regulatory authorities) provided the data are treated confidentially and that the participant's privacy is guaranteed

## **8 SPONSOR RESPONSIBILITIES**

### **8.1 GENERAL DUTIES**

Prior to shipping devices, the study sponsor is responsible for selecting Investigators, obtaining and reviewing copies of IRB/HREC approvals. It is the study sponsor's responsibility to ensure that the study is conducted according to Good Clinical Practice (GCP), the Declaration of Helsinki, and other applicable regulatory requirements, the Study Protocol, or any conditions of approval imposed by the IRB/HREC or local regulatory authorities. Additionally, the study sponsor will ensure proper clinical site monitoring, and ensure study subject informed consent is obtained.

### **8.2 SELECTION OF SITES AND INVESTIGATORS**

The investigators have been selected because of their medical qualifications, education and training, interest in participation, ability to conduct and document the results of the study, ability to accrue participants, and expertise in the therapeutic area.

The sponsor will ascertain the suitability of the Investigator to conduct the study according to applicable guidelines and local regulations.

### **8.3 SITE TRAINING**

The initial training of appropriate clinical site personnel to the study will be the responsibility of the study sponsor or their designee.

### **8.4 DEVICE TRAINING**

Investigators responsible for treating participants with the deployable hook device will receive sufficient training to ensure competence in the execution of all aspects of the procedure. Training will include demonstration videos, didactic presentation, and as may include hands-on experience. Training will also include all of the elements in the Instructions for Use (IFU). Training for first use will be conducted before the first cases, and subsequent cases preceded by refresher training as necessary.

Investigators without prior deployable hook experience will perform up to two (2) training cases, depending on the Investigator comfort level. As well, these Investigators should plan at least 2 stacked cases in one day for good technique adoption.

### **8.5 MONITORING**

#### **8.5.1 Site Monitoring Procedures**

All study monitoring activities will be managed and performed by the Sponsor or designee monitors. eCRFs will be source-document verified according to the monitoring plan. The extent, nature, and frequency of on-site visits will be based on considerations such as study objectives

**Abbreviated CONFIRM Protocol**

and/or endpoints, study design and complexity, and enrollment rate. These tasks will be performed according to relevant SOPs and the detailed study monitoring plan. The detailed monitoring plan will describe who will conduct the monitoring and at what frequency, and distribution of monitoring reports. It will focus on preventing or mitigating non-compliance and identify risks to critical data and processes.

At regular intervals during the study, the study monitors will contact the study sites via on-site visits, video/audio calls, emails and/or letters in order to review the study progress, CRF completion and to address any concerns or questions regarding study conduct. By verifying compliance, these activities will ensure:

- The study is conducted in accordance with the study protocol, relevant Good Clinical Practice (GCP) and International Conference on Harmonization (ICH) guidelines, as well as in conjunction with 21 CFR Part 812, 50, 54, 56 and ISO 14155; Protection of Human Patients (Informed Consent) (21 CFR Part 50), Financial Disclosure by Clinical Investigators (21 CFR Part 54), Institutional Review Boards (21 CFR Part 56), Investigational Device Exemptions (21 CFR Part 812), the Declaration of Helsinki, the privacy requirements of the Health Information Portability and Accountability Act (HIPAA);
- Adequate protection of the rights and safety of the informed patients involved in the study by thoroughly providing accurate and complete data; and
- Quality and integrity of the data.

The frequency and scope of periodic site visits will be determined according to the site performance, enrollment, and public health emergency status. There will be remote or on-site monitoring in advance of data locks in preparation of clinical study reports.

Monitoring activities will include: review of the informed consent process and research authorization confirmation, regulatory document review, overall investigational plan adherence, GCP/ICH compliance, facility assessment, study staff assessment and additional study related functions that contribute to the safety of study Patients and the integrity of study data.

Investigators must provide adequate time and resources to comply with the study protocol and will be available to the study monitor and/or designee via telephone, and in person during site visits. The Investigator will also provide the study monitor with a suitable working environment for review of study-related documents.

